3.5.5 Selection and Timing of Dose for Each Subject

A new PVR will be inserted every 7 days, with up to 10 PVRs used through Week 12 of pregnancy (10 weeks post-oocyte retrieval).

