6.3.3 Visit 6: 2 Weeks After Oocyte Retrieval

Visit 6 will occur 2 weeks (14±2 days) after oocyte retrieval.

The following must take place at the visit:

- Vital signs
- Blood collection for assessment of:
 - Endocrine parameters (progesterone and β -hCG)
If the subject has a negative β -hCG (<5 mIU/mL), treatment will be stopped and the subject will be withdrawn from the trial.
- Removal of PVR2 and insertion of PVR3 (for subjects with a positive β -hCG (\geq 5 mIU/mL))
Insertion of PVR3 can be performed either at the trial site or at home.
- Review of PVR diary
- Assessment of drug accountability
- Recording of any vaginal bleeding noted in the subject's bleeding log since the previous visit
- Assessment of vaginal hemorrhage
- Recording of use of any concomitant medication
- Recording of AEs

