6.4 End-of-trial

The End-of-trial visit (Visit 10) occurs 12 weeks (84 ± 2 days) after oocyte retrieval (week 14 of pregnancy) / 2 weeks (14 ± 2 days) after the last exposure to IMP.

The following end-of-trial procedures / assessments must take place:

- Vital signs

- Blood collection for assessment of:
 - Clinical chemistry and hematology parameters
- Urinalysis
- Complete physical examination (including weight, and BMI calculation)
- Pelvic examination (documentation of presence and grade [intensity] of any pain, irritation, abrasions, or lesions on the cervix or vagina or vaginal adhesions).
If any lesions or abrasions are found on the cervix or vagina or vaginal adhesions are noted, another examination will be performed 2-4 days later.
- TVUS or abdominal ultrasound (pregnant subjects only) to determine the number of gestational sacs with/without fetal heart beat and estimate gestational age
- Recording of any vaginal bleeding noted in the subject's bleeding log since the previous visit
- Assessment of vaginal hemorrhage
- Recording of use of any concomitant medication
- Recording of AEs

After completion of the End-of-trial visit, subjects will be referred to their obstetricians for further care.

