Oocyte retrieval will occur approximately 35-37 hours after hCG administration. On the day after oocyte retrieval, the subject will begin treatment with the investigational medicinal product (IMP), PVR. Following instruction on PVR insertion and removal, the subject will insert the first PVR (PVR1) at the trial site. The PVR will remain in place a minimum of 23 hours/day. The subject will remove PVR1 before embryo transfer and reinsert it after the transfer. Fresh embryo transfer will occur 5 days after oocyte retrieval per the trial site's protocol. The number of embryos to transfer must be guided by the 2017 American Society for Reproductive Medicine (ASRM) and the Society for Assisted Reproductive Technology (SART) guidelines (SART/ASRM 2017): women with the expectation of one or more high-quality embryo(s) available for cryopreservation, and women with previous live birth after an IVF cycle, will have transfer of a single blastocyst. All other women will have transfer of no more than two blastocysts. Additional PVRs will be distributed for weekly insertion, with the second PVR (PVR2) to be inserted at home 7 days following the initial insertion of the first PVR (PVR1), and the third PVR (PVR3) to be inserted either at home or at the site 7 days following the insertion of PVR2.

Two weeks after oocyte retrieval, a blood draw will be performed to measure serum levels of progesterone and  $\beta$ -hCG. Subjects with a  $\beta$ -hCG level  $<5$  mIU/mL will be discontinued from the trial. Those with a  $\beta$ -hCG level  $\geq 5$  mIU/mL will insert their next PVR and continue in the trial for up to a total of 10 weeks (up to a total of 10 PVRs). Additional serum pregnancy tests will be performed at 2 weeks + 3-4 days and at 3 weeks. Subjects who are no longer pregnant will be discontinued from the trial. Subjects with positive  $\beta$ -hCG results at 3 weeks will insert PVR4 and receive PVR5 and PVR6 to be inserted weekly.

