A TVUS will be performed to document the presence of an intrauterine gestational sac 4 weeks + 3-4 days after oocyte retrieval. If it is determined that the subject has an ectopic pregnancy, the subject will be treated according to the site's standard protocol and will be withdrawn from the trial. Six weeks after oocyte retrieval, a TVUS will be performed to determine the presence and number of gestational sacs with/without fetal heartbeat. Pregnant subjects will insert PVR7 and receive additional PVRs to be inserted weekly (PVR8, PVR9, and PVR10). Ten weeks after oocyte retrieval (if the subject is pregnant), an ultrasound (either transvaginal or abdominal) will be performed to determine the number of gestational sacs present with and without fetal heartbeat and the estimated gestational age.

Safety will be monitored throughout the trial. Standardized criteria will be applied to AEs of special interest ([Protocol Section 8.3](#)) to establish grade (intensity). Patient-reported vaginal pain and/or irritation should be recorded as an AE if considered clinically significant by the physician. The physician can perform an unscheduled pelvic examination at his or her discretion based upon these AEs at any time. A scheduled pelvic examination will be performed at screening, on day 1 of PVR treatment, and 4 weeks + 3-4 days, 6, 10, and 12 weeks post-oocyte retrieval (Visits 4, 7P, 8, 9 and 10) to document the presence and grade (intensity) of any pain, irritation, abrasions, or lesions on the cervix or vagina and the presence and grade (intensity) of vaginal adhesions using standardized criteria. If any lesions or abrasions are found on the cervix or vagina or vaginal adhesions are noted, another examination will be performed 2-4 days later. Subjects will be followed until the lesions/abrasions resolve or until the final assessment at the End-of-trial visit, whichever comes first. Any clinically significant finding will be reported as an AE.

Post-trial procedures will be performed 2 weeks after the last exposure to investigational medicinal product (IMP) (12 weeks after oocyte retrieval).

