#### **8.1.1 PVR**

The total number of PVRs used and the duration of treatment will be summarized. Furthermore, the drug compliance rate will also be summarized. Compliance is defined as follows:

(number of PVRs used) / (number of PVRs expected to be used).

The number of PVRs expected to be used is defined to be the number of weeks from oocyte retrieval to either confirmation of no pregnancy via  $\beta$ -hCG test or TVUS assessment or in the case of a subject where there is no such confirmation, the end of trial visit.

The number of times a subject was unable to keep a PVR in for at least 23 hours and the number of times a subject recorded a damaged PVR will be summarized. A detailed associated listing will be produced.

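### For women who stay pregnant, SAP 8.1.1 counts expected rings to week 12 although at most 10 are scheduled, so full use scores about 83%

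*SAP*

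**What the plan says.** SAP 8.1.1 takes compliance as the number of rings used over the number expected. Protocol 9.8.1 gives the same ratio but does not define the denominator. The SAP does: "The number of PVRs expected to be used is defined to be the number of weeks from oocyte retrieval" up to a negative pregnancy finding by β-hCG or ultrasound, or, "in the case of a subject where there is no such confirmation, the end of trial visit". SAP 8.1 plans the summary for the safety and mITT cohorts.

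The treatment schedule is stated elsewhere:

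- SAP 3.1 has women with a positive test "continue in the trial for up to a total of 10 weeks (up to a total of 10 PVRs").
- Protocol 3.5.5 agrees: a new ring every 7 days, "with up to 10 PVRs used through Week 12 of pregnancy (10 weeks post-oocyte retrieval").
- SAP 3.1 places the final visit after treatment has ended: "Post-trial procedures will be performed 2 weeks after the last exposure to investigational medicinal product (IMP) (12 weeks after oocyte retrieval").
- Protocol 6.4 gives the same timing, with a window of 84 ± 2 days: "The End-of-trial visit (Visit 10) occurs 12 weeks" after retrieval.

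**The concern.** The denominator uses elapsed weeks as a stand-in for scheduled rings. The two agree only while rings are being worn. For a woman with an ongoing pregnancy the count continues for about two weeks in which no ring is scheduled, so perfect use cannot score 100%.

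This is not a constant offset that a reader could subtract. At nominal visit times, the count for a woman confirmed not pregnant stops during or at the end of treatment, and full use scores 100%. The score thus depends on pregnancy outcome as well as on ring use. The women marked down are those with the longest exposure, in a trial whose purpose is safety and tolerability.

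**Working it through.** **Inputs**

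- First ring on the day after retrieval, then one every 7 days (Protocol 5.1.1).
- Maximum 10 rings (SAP 3.1; Protocol 3.5.5).
- Visit 9 at 70 ± 2 days after retrieval (Protocol 6.3.8).
- Visit 10, the end-of-trial visit, at 84 ± 2 days (Protocol 6.4).
- Expected rings = weeks from retrieval to Visit 10 if non-pregnancy is never confirmed (SAP 8.1.1).

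**Step 1: reproduce the plan's ring count.** Insertions fall on days 1, 8, 15, 22, 29, 36, 43, 50, 57 and 64 after retrieval. That is 10 rings, the last due out on day 71, which agrees with the stated maximum.

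**Step 2: apply the SAP rule to a woman who stays pregnant and uses all 10.** Compliance = 10 / (days to Visit 10 / 7). The SAP does not say whether part-weeks are rounded, so all three readings are shown.

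| Day of Visit 10 | Weeks | Fractional | Rounded down | Rounded up |
|---|---|---|---|---|
| 82 | 11.71 | 85.4% | 10/11 = 90.9% | 10/12 = 83.3% |
| 84 | 12.00 | 83.3% | 83.3% | 83.3% |
| 86 | 12.29 | 81.4% | 10/12 = 83.3% | 10/13 = 76.9% |

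No cell reaches 100%.

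**Step 3: one ring missed.** 9/12 = 75.0% under the rule, against 9/10 = 90.0% of the rings scheduled.

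**Step 4: compare with women confirmed not pregnant at nominal times, all using every scheduled ring.**

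- Negative test at week 2: 2/2 = 100%.
- Negative test at week 3: 3/3 = 100%.
- Loss found by ultrasound at week 10: 10/10 = 100%.
- Still pregnant at week 10, same 10 rings: 10/12 = 83.3%.

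The last two women used their rings identically.

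**Step 5: check the replacement rule.** Count scheduled insertions up to Visit 9, capped at 10. The tenth insertion is due on day 64, before the earliest Visit 9 (day 68), so the count is 10 on every day from 68 to 72 and full use is 10/10 = 100%. The cap is needed: a program stepping every 7 days would reach day 71 and add an eleventh ring if Visit 9 fell late. Elapsed weeks to Visit 9 would still be inexact: 10/(68/7) = 102.9% and 10/(72/7) = 97.2%.

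For a negative test on day 14 or 15, the third ring is not inserted, because Protocol 6.3.3 makes it conditional: "Removal of PVR2 and insertion of PVR3 (for subjects with a positive" β-hCG result. Expected = 2, and full use = 2/2 = 100%.

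**The case against.** The arithmetic is not in dispute; the case on the other side is about weight and precision.

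- **It is only descriptive.** SAP 8.1.1 also reports total rings used, treatment duration, failures to keep a ring in for 23 hours, damaged rings and a listing. A reader would see 10 rings over about 10 weeks and could work out what happened. This stands, and it limits the consequence. It does not make the printed rate correct.
- **No table by pregnancy outcome is planned.** True. What is reported is a summary over each cohort, which mixes the two groups. Its bias depends on the share of ongoing pregnancies and cannot be derived from the documents.
- **A replacement ring could lift the score.** Protocol 6.3.5 dispenses one, and the SAP does not say whether it counts as used. With 11 rings counted and Visit 10 on day 82 or 83, rounding down gives 11/11 = 100%. So the statement that 100% is out of reach holds for exactly 10 rings. Reaching 100% through a lost or damaged ring would mask the error, not correct it.
- **The comparison group is not always at 100%.** With fractional weeks, two rings and a negative test on day 12 give 2/(12/7) = 116.7%; on day 16, 2/(16/7) = 87.5%. The 100% figures in Step 4 hold at nominal times only. This is further evidence that elapsed weeks are a poor measure of scheduled rings.
- **The replacement rule could misfire when a test falls a day late.** Visit 6 may be on day 16, after the third ring's nominal day 15; Visit 7 may be on day 23, after the fourth ring's day 22. The protocol ties both insertions to a positive result at that visit, so the new wording must exclude a ring withheld for a negative test. The fix below does so.

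**Conclusion.** The rule in SAP 8.1.1 gives a wrong number when followed exactly. A woman who stays pregnant and uses all 10 scheduled rings is reported at 83.3% at the nominal visit time: 81.4% to 85.4% across the visit window with fractional weeks, and 76.9% to 90.9% with whole-week rounding. These figures assume exactly 10 rings counted as used, insertions on schedule, and Visit 10 within 84 ± 2 days. No bias in the cohort mean is claimed. The error is confined to the compliance summary, but it should be corrected before that table is produced.

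**What to change.** Replace the definition in SAP 8.1.1 with a count of scheduled insertions. For a woman confirmed not pregnant, count the insertions due before that confirmation, and do not count a ring withheld because the test was negative. For a woman without such confirmation, end the count at the week-10 Visit 9 instead of the end-of-trial visit. Cap the count at 10 in all cases.

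The same edit could usefully say whether replacement rings count as used, and how a woman who stops early while still pregnant is handled, since Visit 9 also serves as the early-withdrawal visit.

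The cost is one or two sentences and a programming change. The PVR diary already records insertion and removal dates (Protocol 7.3.6), so no new data are needed, and no dose, visit or procedure changes.

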#### **8.1.2 Oral Contraceptives**

In this trial, all subjects will be prescribed the same contraceptives. The total dose and duration of treatment will be summarized. Associated listing will also be generated.

#### **8.1.3 Leuprolide Acetate**

For Leuprolide, a summary of the total dose and duration of treatment will be generated. Furthermore, the start and end date of Leuprolide Acetate from last day of oral contraceptive use will be summarized. Associated listing will be generated.

#### **8.1.4 MENOPUR Administration**

Exposure to MENOPUR will be summarized by the total dose administered and duration of treatment (days). The maximum MENOPUR dose, the dose on stimulation day 1, the final dose, and the number of dose adjustments will also be summarized. Associated listing will be generated.

#### **8.1.5 hCG**

Intramuscular injection of 10,000 IU hCG (NOVAREL) will be administered to induce final follicular maturation. A subject must have at least 2 follicles  $\geq 17$  mm to receive the hCG trigger. The following will be summarized: number of subjects who met the hCG criteria, number of subjects that had hCG administered, number of subjects who met the hCG criteria and had hCG administered, and the number of days from when the hCG criteria was met (the date of final stimulation where at least 2 follicles  $\geq 17$  mm is observed) to when the hCG is administered. Associated listing will be generated.

## 9 Efficacy

### 9.1 General Considerations

All confidence intervals will be two-sided 95% confidence intervals.

### 9.2 Primary Endpoint

The primary endpoint, spontaneous abortion, is defined as two positive  $\beta$ -hCG tests occurring at least two days apart on or after 2 weeks post-oocyte retrieval, but followed by observation of any empty intrauterine gestational sac (blighted ovum), intrauterine gestation without a fetal heartbeat, or absence of viable fetuses, as documented by transvaginal ultrasound (TVUS).

The derivation of this endpoint will be as follows:

- Any subject that has two positive  $\beta$ -hCG tests at least two days apart, and
- meeting at least one of the following conditions at visit 7P (4 weeks and 3-4 days post oocyte retrieval) or at a later visit:
  1. the TVUS assessment at a later visit shows that there is no presence of gestational sac,
  2. there is a presence of empty gestational sac,
  3. there is a gestational sac that has a fetus without a heartbeat, or
  4. any AE of pregnancy loss that meets the definition of spontaneous abortion.

In order to clearly identify AEs that are spontaneous abortions, listing of all AEs related to pregnancy loss, will be generated and provided to the medical team together with the reported and coded terms. [Appendix 3](#) lists the preferred terms associated with pregnancy loss that will be used for generating this listing. This listing will be provided periodically throughout the trial. The medical team will use these listings to identify AEs that meet the spontaneous abortion definition. The identification process will be completed prior to data base lock. Since spontaneous abortion can occur outside of scheduled visits, for accurate accounting of all spontaneous abortions, the AE eCRF page needs to be included.

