### 9.4.4 Positive $\beta$ -hCG

Positive  $\beta$ -hCG is defined as a positive serum  $\beta$ -hCG test at 2 weeks and 2 weeks + 3-4 days post-oocyte retrieval. To allow for assessment that might occur outside the visit window, a subject will be considered to be biochemically pregnant if there are two positive assessment at least two days apart on or after 2 weeks post-oocyte retrieval. The positive  $\beta$ -hCG rate will be derived for subjects in the mITT and safety cohorts for subjects that had oocyte(s) retrieved. Associated 95% confidence intervals for these event rate estimates will also be presented.

Subjects who do not have two  $\beta$ -hCG tests due to missing data, early withdrawal, or any other reason will be counted as not having positive  $\beta$ -hCG unless a positive result is observed at a later pregnancy assessment. For example, if the outcome of these  $\beta$ -hCG tests is missing and a TVUS confirms clinical pregnancy at a later date then  $\beta$ -hCG will be imputed as 'positive'.

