#### **9.4.5 Clinical Pregnancy**

Clinical pregnancy is defined as a TVUS showing at least 1 intrauterine gestational sac with fetal heartbeat at 6 and 10 weeks (i.e., up to 42 and 70 days) post-oocyte retrieval. The frequency and proportion of subjects that are clinically pregnant at 6 and 10 weeks post-oocyte retrieval will be derived for subjects in the mITT and safety cohorts for subjects that had oocyte(s) retrieved. Associated 95% confidence intervals for these event rate estimates will also be presented.

For the clinical pregnancy rate derivation at 6 weeks post-oocyte retrieval, if a subject has missing TVUS assessment and no other TVUS assessment at a later date, the subject will be counted as not having a clinical pregnancy. In contrast, if there is a later assessment with at least 1 intrauterine gestational sac with fetal heartbeat, the subject will be imputed as having a clinical pregnancy at 6 weeks post-oocyte retrieval.

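### The primary endpoint derivation has no rule for missing β-hCG tests, so a woman counted as pregnant by imputation can have a documented loss that is not a primary event

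*SAP*

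**What the plan says.** **Primary endpoint (SAP 9.2).** An event needs two things together. The first is "Any subject that has two positive" β-hCG tests at least two days apart. The second is "meeting at least one of the following conditions at visit 7P" or later: no sac, an empty sac, a fetus without a heartbeat, or, as item 4, "any AE of pregnancy loss that meets the definition of spontaneous abortion". Protocol 7.1.2 and 9.7.2 carry the same two-test definition. None of these sections, nor SAP 9.3, says what happens if β-hCG results are missing.

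**Positive β-hCG rate (SAP 9.4.4; protocol 9.7.3.4).** Women without two tests "will be counted as not having positive" β-hCG "unless a positive result is observed at a later pregnancy assessment". The SAP's example is that if the outcome of these "tests is missing and a TVUS confirms clinical pregnancy at a later date then" β-hCG is set to positive.

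**Clinical pregnancy (SAP 9.4.5).** This rests on ultrasound alone. If the 6-week scan is missing but a later one shows a sac with heartbeat, "the subject will be imputed as having a clinical pregnancy at 6 weeks post-oocyte retrieval".

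**The concern.** The plan expects that some β-hCG results will be missing and handles this for the secondary positive β-hCG rate, but not for the primary endpoint. Take a woman with fewer than two recorded positives whose scan shows a heartbeat. She is counted as β-hCG positive and as clinically pregnant. If a later scan before Week 12 shows that the heartbeat has gone, she meets a loss condition but fails the two-test condition, so she is a non-event.

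The adverse event item does not rescue her. It is one of the loss conditions and so sits under the same 'and'. It also asks for an event that meets the spontaneous abortion definition, which again requires two positive tests.

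The error runs in one direction. She stays in the denominator and her loss leaves the numerator. In a safety trial that asks whether the upper confidence bound excludes 15%, this is the anti-conservative direction.

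**Working it through.** **Inputs from the documents.** N = 240 in the mITT cohort, threshold 15%, two-sided exact 95% interval, stated power 81.8% at a true rate of 9% (SAP 3.3, Table 2). Three scheduled tests, at Visits 6, 6P and 7 (protocol 7.1.1.1). Any two positives at least two days apart qualify (SAP 9.2).

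**Step 1: reproduce the plan's figure.** The exact upper bound for x events is the 0.975 quantile of Beta(x + 1, 240 − x).

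- 25/240 (10.42%): upper bound 14.99%, excludes 15%.
- 26/240 (10.83%): upper bound 15.47%, does not.

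The trial therefore excludes 15% with at most 25 events. P(X ≤ 25 | 240, 0.09) = 81.3%, against 81.8% from the plan's simulation. The other eight cells of Table 2 also agree, within 0.6 points. At a true 15%, P(X ≤ 25 | 240, 0.15) = 2.48%.

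**Step 2: how many women could be affected.** One missed test usually changes nothing, because two others remain. The gap usually needs at least two of three tests missing. The documents give no rate of missed tests, so I assume each is missed independently with probability q:

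m = 3q²(1 − q) + q³

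**Step 3: effect on the primary analysis at a true 15%.** Expected losses are 240 × 0.15 = 36. Hidden losses are 36m. The counted rate is 0.15(1 − m), and the false-exclusion chance is P(X ≤ 25 | 240, 0.15(1 − m)).

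| q (assumed) | m | hidden of 36 losses | chance of excluding 15% |
|---|---|---|---|
| 0 | 0 | 0 | 2.48% |
| 1% | 0.03% | 0.01 | 2.49% |
| 2% | 0.12% | 0.04 | 2.52% |
| 5% | 0.7% | 0.26 | 2.76% |
| 10% | 2.8% | 1.0 | 3.69% |

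**Step 4: why step 2 says 'usually'.** The definition at the start of SAP 9.2 counts tests only from 2 weeks after retrieval, while protocol 6.3.3 allows Visit 6 at 14 ± 2 days. The derivation bullet below that definition omits the limit. If the limit is applied, a Visit 6 test on day 12 or 13 does not count, and for those women one further missed test is enough: 1 − (1 − q)² = 2.0%, 4.0%, 9.8% or 19% for the same q. How many women would have an early Visit 6 is not stated, so this is not added to the table.

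**The case against.** The strongest reply is that a woman who follows the protocol can hardly fall into the gap. Three tests are scheduled, and protocol 6.3.3 and 6.3.5 tie insertion of PVR3 and PVR4 to a positive result at Visits 6 and 7. A woman who continues as written should already have two positives about a week apart. This stands, and it is why the expected effect is small. It does not remove the point, because SAP 9.4.4 is written for women whose tests are missing and who are later found pregnant.

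A second reply is that the loss remains visible. Protocol 8.3.7 records pregnancy losses as adverse events, and under SAP 9.2 the medical team reviews a listing of them before database lock. That review would probably expose the case. However, nothing written lets the team waive the two-test condition, and an unwritten waiver would be a case-by-case decision on the primary endpoint of an open-label trial.

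Third, SAP section 2 bases the assessment on the totality of safety information and does not tie success to the primary objective. That is true, but the comparison with 15% is still the prespecified primary analysis.

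Two stronger readings are tempting:

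- A reader might infer that the two rules contradict each other. They govern different endpoints, so this is inconsistent handling of missing data, not a contradiction.
- A reader might infer that false exclusion becomes 3.9% or 5.8%. These are P(X ≤ 26) and P(X ≤ 27) at 15%, and they hold only if exactly one or two losses are hidden. Nothing in the documents supports that many, and 3.9% is above even the 10% row of the table.

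**Conclusion.** The point holds as a gap in the missing-data handling of the primary endpoint. As written, the derivation can turn a documented pregnancy loss into a non-event because laboratory results are missing, although the same plan counts the woman as pregnant.

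The expected size is small: the false-exclusion chance at a true 15% moves from 2.48% to between 2.49% and 3.69% for 1% to 10% of tests missed. This rests on independent missed tests, missingness unrelated to loss, and two of three tests having to be missing. None of these can be checked from the documents. The direction does not depend on them: the gap can only lower the rate. At 25 against 26 counted events, a single such loss would decide the result. The planned sample size and the power table are not in question.

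**What to change.** Add to SAP 9.2: only when fewer than two β-hCG results are available because tests are missing, an intrauterine pregnancy documented by ultrasound satisfies the β-hCG condition, and this applies to the adverse event item as well. The restriction to missing tests matters; without it, the scan would override the two-test rule for women who were tested. State also that a sac without a heartbeat is enough for this purpose. The example in SAP 9.4.4 speaks of clinical pregnancy, which requires a heartbeat, and would leave out a blighted ovum, which belongs to the primary endpoint.

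Align protocol 7.1.2 and 9.7.2, and the notes in section 2.2 of both documents that repeat the definition. Report how many events were counted through this rule, and give the strict two-test count with its exact interval as a sensitivity analysis. The SAP change log says that endpoints were aligned with DR-PGN-302, and the strict count keeps the current definition available for that comparison.

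The cost is a small clarification of the primary endpoint derivation, the matching protocol text, and possibly a slightly higher observed rate. No new data are needed and N stays the same. It should be settled before database lock.

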6.3.6 Visit 7P: Procedural Visit

Subjects will attend a procedural visit (Visit 7P), one week + 3-4 days after Visit 7.

The following must take place at the visit:

- TVUS to document the presence of an intrauterine gestational sac.
In case of an ectopic pregnancy the subject will be treated according to the site's standard protocol. Treatment with PVR will be stopped and the subject will be withdrawn from the trial and the early withdrawal visit is to occur (section 6.3.8).
- Pelvic examination (documentation of presence and grade [intensity] of any pain, irritation, abrasions, or lesions on the cervix or vagina or vaginal adhesions).

If any lesions or abrasions are found on the cervix or vagina or vaginal adhesions are noted, another examination will be performed 2-4 days later.

- Review of PVR diary
- Recording of any vaginal bleeding noted in the subject's bleeding log since the previous visit
- Assessment of vaginal hemorrhage
- Recording of use of any concomitant medication
- Recording of AEs

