6.3.7 Visit 8: Week 8 of Pregnancy (6 Weeks After Oocyte Retrieval)

Subjects will attend Visit 8, 6 weeks (42±2 days) after oocyte retrieval.

The following must take place at the visit:

- Vital signs
- TVUS to determine the presence and number of gestational sacs with/without fetal heart beat
- Pelvic examination (documentation of presence and grade [intensity] of any pain, irritation, abrasions, or lesions on the cervix or vagina or vaginal adhesions).
If any lesions or abrasions are found on the cervix or vagina or vaginal adhesions are noted, another examination will be performed 2-4 days later.
- Recording of any vaginal bleeding noted in the subject's bleeding log since the previous visit
- Assessment of vaginal hemorrhage
- Removal of PVR6 and insertion of PVR7.
Insertion of PVR7 can be performed either at the trial site or at home.
- Review of PVR diary
- Assessment of drug accountability
- Recording of use of any concomitant medication
- Recording of AEs
- Dispensing of IMP: the next 3 PVRs (PVR8, PVR9, and PVR10) will be distributed.
will be distributed.
The subjects will remove and insert the PVRs at home. Subjects will be instructed to replace the PVR every 7 days.

6.3.8 Visit 9: Week 12 of Pregnancy (10 Weeks After Oocyte Retrieval) / Early-withdrawal Visit

Visit 9 will occur 10 weeks (70 ± 2 days) after oocyte retrieval. If a subject discontinues the trial prematurely an Early-withdrawal visit should be scheduled as soon as possible and within 1 week after last dose of the IMP.

The following procedures / assessments must take place at Visit 9 / the Early-withdrawal visit, irrespective of whether the subject discontinues the trial prematurely or continues:

- Vital signs
- Blood collection for assessment of:
 - Clinical chemistry and hematology parameters
 - Endocrine parameters (progesterone)
- Urinalysis
- Complete physical examination (including weight and BMI calculation)
- Pelvic examination (documentation of presence and grade [intensity] of any pain, irritation, abrasions, or lesions on the cervix or vagina or vaginal adhesions).
If any lesions or abrasions are found on the cervix or vagina or vaginal adhesions are noted, another examination will be performed 2-4 days later.
- TVUS or abdominal ultrasound (pregnant subjects only) to determine the number of gestational sacs with/without fetal heart beat and estimate gestational age
- Recording of any vaginal bleeding noted in the subject's bleeding log since the previous visit

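### SAP 9.2 makes one empty-sac or no-heartbeat finding at Visit 7P a permanent primary event, even if the same sac shows a heartbeat at Visit 8

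*SAP*

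**What the plan says.** SAP 9.2 derives the primary endpoint in two steps. The woman needs two positive β-hCG results separated by two days or more. She then becomes an event on "meeting at least one of the following conditions at visit 7P (4 weeks and 3-4 days post oocyte retrieval) or at a later visit". Condition 2 is "there is a presence of empty gestational sac". Condition 3 runs "there is a gestational sac that has a fetus without a heartbeat, or", its last word leading on to condition 4, a pregnancy-loss adverse event that fits the definition. No sentence asks for a second scan, and none removes the event if a later scan shows a heartbeat. The medical review in that section concerns adverse events: "The medical team will use these listings to identify AEs that meet the spontaneous abortion definition". It is not described as checking or reversing events that come from scans.

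The protocol gives its scans different tasks. At Visit 7P (Protocol 6.3.6) it is "TVUS to document the presence of an intrauterine gestational sac". Heartbeat enters at Visit 8 (Protocol 6.3.7): "TVUS to determine the presence and number of gestational sacs with/without fetal heart beat". Protocol 7.1.1.2 repeats this split. SAP 9.4.5 starts the clinical pregnancy endpoint at the same point: "Clinical pregnancy is defined as a TVUS showing at least 1 intrauterine gestational sac with fetal heartbeat at 6 and 10 weeks".

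**The concern.** The SAP can take a verdict of non-viability from a scan that the protocol did not set up to judge viability. The only 7P finding that Protocol 6.3.6 names as leading to withdrawal is an extrauterine pregnancy: "In case of an ectopic pregnancy the subject will be treated according to the site's standard protocol". A woman with an empty sac, or a fetus without a heartbeat, can therefore reach Visit 8 and show a heartbeat there. The derivation would still hold her as a loss.

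The same false event would enter the 6- and 10-week loss rates (SAP 9.4.1), the Bayesian sensitivity analysis (SAP 9.3.2) and the bleeding-log exclusions around a loss (SAP 10.4.1). At stake is a primary safety rate, compared with 15%, that could include continuing pregnancies.

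**Working it through.** **1. Timing.** Visit 7 is at 21±2 days after retrieval (Protocol 6.3.5), and Visit 7P follows 10 to 11 days later (Protocol 6.3.6). Earliest: 19 + 10 = 29 days. Latest: 23 + 11 = 34 days. SAP 9.2 places it nominally at 4 weeks + 3-4 days, i.e. 31-32 days. Table 6-1, footnote b, starts pregnancy 2 weeks before retrieval, so 29 days is 29 + 14 = 43 days, or 6 weeks + 1 day. Visit 8 is at 42±2 days.

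**2. One woman under both rules.** Suppose 7P records an empty sac and Visit 8 shows a heartbeat in that sac.
- SAP 9.2: condition 2 is met at 7P and not cancelled, so she is a spontaneous abortion.
- SAP 9.4.5: a sac with a heartbeat at 6 weeks, so she is a clinical pregnancy.

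SAP 9.4.5 does let a later scan inform the 6-week status when that scan is missing. SAP 9.2 has no counterpart.

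**3. The plan's own power.** Inputs from SAP 3.3 and 9.3.1: n = 240, exact two-sided 95% interval, success if the upper bound is below 15%. The upper bound for x events is the 0.975 quantile of Beta(x + 1, n − x).
- x = 25: 14.99%, passes.
- x = 26: 15.47%, fails.

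Power is P(X ≤ 25) for X ~ Binomial(240, p).

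| True rate | SAP Table 2 | Exact |
|---|---|---|
| 8% | 93.1% | 92.9% |
| 9% | 81.8% | 81.3% |
| 10% | 63.2% | 63.6% |

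The stated figures reproduce within simulation error.

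**4. Margin.** At 9%, 0.09 × 240 = 21.6 events are expected, which leaves 25 − 21.6 = 3.4 to the cut-off. One false event can turn 25/240 into 26/240.

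**5. Illustration.** Let q be the share of the mITT cohort wrongly kept as events, added to the true rate: power = P(X ≤ 25) at p + q. The documents give no value for q, so the range below is an assumption.

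| q | Women of 240 | Power, true 8% | True 9% | True 10% |
|---|---|---|---|---|
| 0 | 0 | 92.9% | 81.3% | 63.6% |
| 0.5% | 1.2 | 87.9% | 73.0% | 53.6% |
| 1% | 2.4 | 81.3% | 63.6% | 43.7% |
| 2% | 4.8 | 63.6% | 43.7% | 26.1% |

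**The case against.** The strongest reply is that the problem may never arise in the data. If the 7P page records only whether a sac is present, conditions 2 and 3 cannot fire there. Protocol 10.1 lists the visits whose ultrasound results must be in the source documents, and 7P is not among them. This stands as a limit on frequency, since the eCRF is not shown. It does not clear the text: the list in 10.1 is a minimum, and SAP 9.2 itself names 7P as the first visit at which the conditions apply.

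Other points also stand:
- A reader might infer that any sac without a visible heartbeat at 7P counts. It does not. Condition 2 needs an empty sac and condition 3 a fetus, so a sac that is neither recorded as empty nor shown to hold a fetus meets neither.
- The gap is not the SAP's alone. The definition in Protocol 2.2, 7.1.2 and 9.7.2 has no earliest scan visit and no reversal either.
- Day 29 needs both visit windows at their early ends; the nominal visit is later.
- The illustration assumes that the 9% contains no such events. The SAP change log says that endpoints were aligned with DR-PGN-302. If the planning rate came from the same derivation, adding q would count them twice. The documents do not settle this.
- Protocol 2 and SAP 2 say that the trial's success is not tied to the primary objective.

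**Conclusion.** The defect is in the rule as written: followed literally, it can class one woman as both a loss and a clinical pregnancy. It needs correcting before database lock, but its effect on this trial cannot be sized from the documents. The falls in power rest on an assumed q, on 7P findings being recorded, and on a planning rate free of such events.

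A reader might go further and infer that the primary rate is inflated by a known amount, that the ring could look safer than it is, or that the sample size is wrong. None of these is supported. No frequency is given. False events can only raise the observed rate, so they cannot help to exclude 15% wrongly. The stated power is right for its own inputs.

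**What to change.** In SAP 9.2, with matching wording in the protocol's endpoint definition, state that a condition 2 or 3 finding at Visit 7P is not an event if a later ultrasound shows a fetal heartbeat in that same sac.

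- **Apply it per sac.** Up to two blastocysts may be transferred (Protocol 7.3.10), and the definition covers any empty sac. A per-woman reversal could erase a real loss beside a viable twin. State whether loss of one sac beside a viable one counts.
- **No later scan.** The 7P finding stays an event by default, unless medical review before database lock documents a continuing pregnancy. Requiring an adverse-event record instead could drop losses seen on a scan, because Table 6-1, footnote j, waives the ultrasound at early withdrawal for a woman no longer pregnant.
- **Report** the number of subjects reclassified, and the rate without reclassification as a sensitivity analysis.

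The cost is wording in both documents, one programming check and a few medical reviews. No new visit or scan is needed.
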